16.2.3.4. Dose Expansion Weekly Dosing Schedule for Lymphomas

Time and Events Table for Full Study (Cycle = 28 days)									
Study Assessments ¹	Screen ²	Day 1 C1	Day 8 C1	Day 15 C1	Day 1 C2	Day 15 C2	D1 of C3-C16	End of Study Treatment	3-Month Off-study Follow-up
Informed Consent	X								
Baseline Demographics	X								
Medical History	X								
Physical Exam	X	X			X		At the start of each cycle	X	
Ocular Exam	X ³				X ⁴		At the start of each cycle ⁴	X ⁴	
ECOG Performance Status	X				X		At the start of each cycle	X	
Vital Signs (BP, HR, Body Temperature)	X	X ⁵	X ⁵	X ⁵	X ⁵		At the start of each cycle ⁵	X	
Weight and Height	X	Weight only			Weight only		Weight only - At the start of each cycle	Weight	
Hematology	X	X ⁶	X	X	X		At the start of each cycle	X	
Clinical chemistry	X	X ⁶	X	X	X	X	At the start of each cycle	X	
Urine Dipstick	X	X ⁶			X		At the start of each cycle	X	
INR, PTT	X	X ⁶	X	X	X		At the start of each cycle		
HBV/HCV tests	X								
CK-MB , Troponin	X ⁷		X ⁷		X ⁷		At the start of each cycle ⁷	X ⁷	
BNP	X ⁸								
24 hr urine protein and albumin	X				X		At the start of each cycle		
IgG, IgM, IgA	X				X		At the start of every other cycle		
CRP, beta2 microglobulin	X				X		At the start of each cycle		
Pregnancy Test	X ⁹						At the start of cycles 5 ⁹ , 9 ⁹ , 13 ⁹	X ⁹	X ¹⁰
Chest X-ray	X								
12-lead ECG	X ¹¹	X ¹¹	X ¹¹	X ¹¹	X ¹¹		At the start of each cycle ¹¹	X ¹¹	
LVEF and valves assessment (ECHO)	X ¹²						At the start of cycles 4 ¹² , 9 ¹²	X ¹²	

Time and Events Table for Full Study (Cycle = 28 days)									
Study Assessments ¹	Screen ²	Day 1 C1	Day 8 C1	Day 15 C1	Day 1 C2	Day 15 C2	D1 of C3-C16	End of Study Treatment	3-Month Off-study Follow-up
Serum (soluble BCMA)		X ¹³	X ¹³	X ¹³	X ¹³			X ¹³	
Serum (cytokines/chemokines)		X ¹⁴	X ¹⁴	X ¹⁴	X ¹⁴		Predose and EOI on D1 of each cycle	X	
Serum (anti-drug-antibodies)		X ¹⁵		X ¹⁵	X ¹⁵		At the start of cycles 3 ¹⁵ , 6 ¹⁵ , 9 ¹⁵ , 12 ¹⁵ and 16 ¹⁵	X	
Plasma-cfDNA		X						X	
Peripheral blood (flow for TBNK)		X ¹⁶	X ¹⁶		X ¹⁶		At the start of each cycle ¹⁶	X ¹⁶	
Sparse PK (blood)		X ¹⁷	X ¹⁷	X ¹⁷	X ¹⁷	X ¹⁷	C3D1 ¹⁷ , C3D15 ¹⁷ and C5D1 ¹⁷ only	X ¹⁸	
Genetics sample		X ¹⁹							
CT/PET Scan for disease assessments	X ²⁰						At the start of Cycles 3, 5, 7, 9, 11, 13, and 16		
Premedication if needed		X	X	X	X ²⁴	X	Each dosing week		
GSK2857916 administration		X ²¹	X ²¹	X ²¹	X ^{21, 24}	X	Each dosing week ²¹		
Steroid eye drops		X ²²	X ²²	X ²²	X ^{22, 24}	X ²²	Each dosing week ²²		
Tumor biopsy for BCMA expression	X ²³								
Adverse Events		Continuous							
Concomitant Medications	X	Continuous							
Survival Status									X ²⁵
Subsequent Treatment									X ²⁵

1. Assessments scheduled on days of dosing should be done prior to drug administration, unless otherwise specified. All other assessments can be done ± 3 days unless otherwise specified
2. All Screening assessments must be performed within 14 days prior to first dose unless otherwise specified. Informed Consent must be signed before any study-specific assessments are performed.
3. Screening examination to include BCVA (best-corrected visual acuity), slit lamp examination (with special focus on cornea), intraocular pressure, and dilated fundoscopic examination may be performed within 21 days prior to first dose.
4. On-study exams, to include BCVA (best-corrected visual acuity) and slit lamp examination (with special focus on cornea); window for exams is up to 3 days prior to dosing. In the event that a subject has a dose delay due to a non-ocular toxicity and an ocular exam has been performed for that cycle, a repeat ocular exam 3 days prior to dosing may be omitted if the participant did not have corneal signs on the previous exam and does not have any new corneal symptoms.

5. On initial (first infusion) dosing day, vital signs must be assessed at pre-dose (within 30 minutes prior to SOI), +10 minutes and +30 minutes after SOI (± 5 min), EOI, and 1 hour post EOI. On subsequent dosing days, vital signs must be assessed at pre-dose (within 30 minutes prior to SOI), +30 minutes after SOI, and EOI. **On days where vital sign timepoints align with PK sampling timepoints, vital signs should be assessed prior to PK samples being drawn.**
6. If completed within 72 hrs prior to the first dose, this assessment need not be repeated on Day 1 of Cycle 1. Refer to Table 15 of the protocol for comprehensive list of lab tests.
7. Troponin will be measured at the local (troponin I or T) and central (troponin I) lab. CK-MB at the local lab, or if not available by a central laboratory.
8. BNP to be measured locally, or if not available by a central laboratory, at screening; if cardiac workup is required due to safety concerns during the study, BNP should be measured.
9. Perform only in women of child-bearing potential. A serum pregnancy test should be performed at screening, and subsequent pregnancy tests may be either serum or urine
10. Final pregnancy test (serum or urine) must be performed in women of childbearing potential 60 days after last study treatment.
11. On dosing days, perform triplicate ECGs at predose (within 30 minutes prior to SOI) and EOI. **On days where ECG timepoints align with PK sampling timepoints, ECGs should be performed prior to PK samples being drawn (PK sample should be taken at the exact nominal time; refer to footnote 17).** At screening and End of Study, obtain a single ECG measurement.
12. At Screening, LVEF may be performed within 30 days prior to first dose. All ECHOs indicated on dosing days may be performed up to 7 days before dosing. ECHOs to be done locally and sent to GSK for central imaging storage.
13. A single sample for sBCMA will be collected at C1D8 predose, and at the End of Study visit. sBCMA samples will also be collected on C1D1 at predose (within 30 minutes prior to SOI) and EOI (± 5 minutes). On C1D15 and C2D1 collect at predose (within 30 minutes prior to SOI) and EOI (± 5 minutes)
14. Collect cytokines at predose (within 30 minutes prior to SOI) and EOI (± 5 min) (even when infusion is interrupted or halted) to assess allergic reaction.
15. All ADA samples will be collected prior to each infusion.
16. Sample(s) collected for analysis by central lab.
17. PK samples to be taken for both GSK2857916 and cys-mcMMAF measurement at C1D1 predose (within 30 minutes prior to SOI), EOI (just before EOI), 1 hour post EOI (± 5 min), and 3 hours post EOI (± 5 min); predose (within 30 minutes prior to SOI) and EOI (just before EOI) on C1D8, C1D15, C2D1, C2D15, C3D1, C3D15, and C5D1.
18. Collect 1 PK sample at each subject's final visit.
19. Informed consent for optional genetics research should be obtained before collecting a sample.
20. CT/PET scans from within 21 days prior to first dose are acceptable.
21. Study drug administration ± 1 day window only.
22. Prophylaxis with prednisolone phosphate 1% or dexamethasone 0.1% 1 drops QID x 4 days starting 1 day prior to treatment.
23. Archived or fresh tissue required for BCMA testing. Refer to Section 5.2.1 of the protocol Inclusion Criterion #4 for eligibility criteria.
24. Also applies to C2D8.
25. Record subject's survival status and whether subsequent treatment for disease was given. Subject does not need to come in for visit.

Abbreviations:

ADA = Antibody Drug Antibody; ALP = alkaline phosphatase; BCVA = best corrected visual acuity; BNP = B-type natriuretic peptide; C1D1 = Cycle 1 Day 1, etc.; cfDNA = Circulating free DNA; CK = creatine kinase; CRP = C-reactive protein; EOI = End of Infusion; PD = Pharmacodynamics; PK = Pharmacokinetics; QID = 4 times a day; SOI = start of infusion

16.3. Appendix 3: Assessment Windows

No assessment windows will be applied.

16.4. Appendix 4: Study Phases and Treatment Emergent Adverse Events

16.4.1. Study Phases

Study Phase	Definition
Pre-Treatment	Date ≤ Study Treatment Start Date
On-Treatment	Study Treatment Start Date < Date

Some datasets include the first dosing day as On-Treatment and some exclude the first dosing date as On-Treatment. The first dosing day (Day 1) is considered Pre-Treatment for ECOG, ECG, vital signs, liver events, lab tests, cardiac scan, and other safety domains. The first dosing day (Day 1) is considered to be On-Treatment for adverse events and concomitant medications.

16.4.1.1. Study Time Periods for Concomitant Medications and Blood and Blood Supportive Care Products

Concomitant Medication and Blood and Blood Supportive Care Product start and end dates will be assigned to study time periods in relation to first dose of study treatment as defined below. The start date references time flag variables and end date reference time flag variables will be added to the concomitant medications and blood and blood supportive products datasets, respectively.

- **Start relative to treatment:** Assign to 'BEFORE' if start date is prior to study treatment start date or if subject has not taken any study treatment or (start date is missing and end date is before study treatment start date). Else assign to 'DURING' if the start date falls into the on-therapy period as defined above or if subject is ongoing (not all study treatment discontinuation records completed) or start date is missing. Else assign to 'AFTER' if start date is after the on-therapy period.
- **End relative to treatment:** Assign to 'BEFORE' if end date is prior to study treatment start date or if subject has not taken any study treatment. Else assign to 'DURING' if start date falls into the on-therapy period or if subject is ongoing (not all study treatment discontinuation records completed) or (end date is missing and start relative to treatment not 'AFTER'). Else assign to 'AFTER' if start date is after the on-therapy period or (end date is missing and start relative to treatment='AFTER').

Only on-therapy blood and blood supportive care products that start after the start of study treatment are included in the Blood Products and Blood Supportive Care Product summaries. Therefore, for summary tables, include blood and blood supportive care product records where start relative to treatment in ('DURING') and end relative to treatment in ('DURING','AFTER'). All data will be reported in listings.

Concomitant medication start relative to treatment and end relative to treatment flags are used to select data to include in the Concomitant Medication summaries as follows:

- **Summary of Concomitant Medications:** This summary will contain medications including those with start date prior to study treatment start date and continue

(missing end date or end date after study treatment start date) on therapy. Note that any medications with start date and end date prior to study treatment start date will be excluded. In addition, any medication that was started during post-therapy will be excluded. Include concomitant medication records where start relative to treatment in ('BEFORE','DURING') and end relative to treatment in ('DURING','AFTER').

- Summary of Concomitant Medications with On-Therapy Onset: This summary will contain medications with start date after study treatment start date. In addition, any medication that was started during post-therapy (see above for definition of post-therapy) will be excluded. Include concomitant medication records where start relative to treatment in ('DURING') and end relative to treatment in ('DURING','AFTER').

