33. Optional follow-up telephone interview to explore visual symptoms and changes in symptoms and related impacts following treatment discontinuation be performed at least 6 months following the End of Study Treatment visit. This interview would only be for those subjects who experienced corneal symptoms during treatment and consent to participate.
34. End of treatment visit should be performed within 30 days (+7 days) after the last dose or prior to the start of new anti-cancer treatment, whichever is earlier. In cases where more than 30 days (+7 days) have elapsed from the date of the subject's last dose due to dosing delays and a subsequent decision to take the subject off treatment, the end of study treatment visit should be scheduled as soon as possible to allow the final assessments to be performed at the earliest date.

35. Participants with corneal signs or symptoms at the end of study treatment visit should be monitored by ophthalmic exam once a month after the last study dose until deemed clinically stable by an eye care professional complete resolution or for 12 months (whichever comes first). Corneal exams to include BCVA and slit lamp examination (with special focus on cornea). Participants who have completed treatment or the 3 month follow up visit (end of study) will be re-consented for additional ophthalmology follow up.

Abbreviations:

ADA = Antibody Drug Antibody; ALP = alkaline phosphatase; BCVA = best corrected visual acuity; BNP = B-type natriuretic peptide; C1D1 = Cycle 1 Day 1, etc.; cfdNA = Circulating free DNA; CK = creatinine kinase; CRP = C-reactive protein; EM = extramedullary; EOI = End of Infusion; FLC = free light chain; PD = Pharmacodynamics; PK = Pharmacokinetics; QID = 4 times a day; SOI = start of infusion; SPEP = serum protein electrophoresis; UPEP = urine protein electrophoresis

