16.4.2. Treatment Emergent Flag for Adverse Events

Flag	Definition
Treatment Emergent	
 • Study Treatment Start Date \leq AE Start Date • AE Start Date is missing

NOTES:

- If the study treatment stop date is missing, then the AE will be considered to be On-Treatment.
- Time of study treatment dosing and start/stop time of AEs should be considered, if collected.

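### On-Treatment has no end date, so the SAP's AFTER category and its exclusion of post-therapy medications and blood products cannot work as written

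*SAP*

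**What the plan says.** Section 16.4.1 lists two phases. Pre-Treatment is "Date ≤ Study Treatment Start Date" and On-Treatment is "Study Treatment Start Date < Date". Day 1 is moved into On-Treatment for AEs and concomitant medications. Neither definition uses the last dose, a follow-up interval or the start of new anti-cancer therapy.

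Section 16.4.1.1 builds the medication and blood-product flags on this. For start dates: "Else assign to 'DURING' if the start date falls into the on-therapy period as defined above", and then "Else assign to 'AFTER' if start date is after the on-therapy period". It excludes medications begun post-therapy, with the pointer "see above for definition of post-therapy", and limits the blood-product summaries to on-therapy products. Section 6.6 likewise selects records by an on-therapy window.

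Section 16.4.2 flags an AE as treatment-emergent if it starts on or after the treatment start date, or if its start date is missing. A note adds: "If the study treatment stop date is missing, then the AE will be considered to be On-Treatment".

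**The concern.** Several rules presuppose that the on-therapy period closes, but nothing in the SAP closes it. A programmer must either apply 16.4.1 literally, in which case the promised exclusion does nothing, or invent a cut-off. Two programmers could produce different tables from the same data.

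Safety and tolerability are the primary objective. Transfusions, growth factors and other medications given on the next myeloma regimen would be reported as use during GSK2857916 treatment. The AE flag has the same one-sided form, so the question extends to AEs and to worst-case safety results.

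**Working it through.** No plan figure is involved. The check applies the written date rules and looks for any end to the period.

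**Is there an end elsewhere?**
- Section 16.3 applies no assessment windows.
- Section 16.5.2 includes unscheduled visits in worst-case analyses and states no end.
- Section 8.3 splits deaths at 30 days after last dose, for the death table only.
- Footnote 34 of the Part 2 myeloma schedule (16.2.3.1) sets the end-of-treatment visit "within 30 days (+7 days) after the last dose or prior to the start of new anti-cancer treatment, whichever is earlier". Footnote 26 of the 3-weekly lymphoma schedule (16.2.3.3) does the same. These are visit-scheduling rules and are not linked to the phase or the flags. The Part 1 3-weekly schedule (16.2.2.1) has no such footnote.

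**Can AFTER be reached?** For a treated subject:
- A known start date before first dose gives BEFORE.
- A known start date later than first dose satisfies the On-Treatment rule and gives DURING.
- A missing start date gives BEFORE or DURING.

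Nothing is left for AFTER. The end-date version of AFTER needs either a start date after the on-therapy period or a start flag of AFTER, so it is empty too.

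**Illustration (assumed days).** Four doses at 21-day intervals put the last dose on Day 1 + 3 × 21 = Day 64. Suppose new anti-cancer therapy starts on Day 100 and a transfusion or medication starts on Day 150. That is 150 − 64 = 86 days after last dose and 150 − 100 = 50 days into the new regimen. Because 150 > 1, both the start and end flags are DURING, and the record enters the on-therapy summary. Any other day after first dose gives the same result.

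**The end-date rule.** In 16.4.1.1 the end flag tests the start date for DURING and AFTER. Take a discontinued subject with a medication begun 30 days before first dose and stopped on Day 40 (assumed days):
- BEFORE fails, because the end date is not before treatment start.
- DURING fails, because the start date is outside the on-therapy period, the subject is not ongoing and the end date is present.
- AFTER fails, because the start date is not after the period and the end date is present.

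The record has no end category. The concomitant-medication summary requires DURING or AFTER, so the record is dropped. The text of the same section says a medication begun earlier and ending after treatment start belongs in that summary.

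**The AE flag.** An AE starting on Day 150 meets the rule in 16.4.2. The note on a missing stop date modifies nothing, because the flag never uses a stop date.

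**The case against.** The strongest reply is that the AE rule may be deliberate and its consequences small. A flag with only a lower bound is a defensible conservative choice in a first-in-human study with corneal toxicity followed for up to 12 months. The AE collection period is normally set in the protocol, which is not shown. Section 8.1 does not say that its tables are filtered by the flag, so late AEs that are collected would appear either way. Section 6.6 also speaks of blood products used after the start of study medication, which can be read as open-ended. All AEs and blood products are listed in any case. Most of this stands for AEs, but none of it supplies the post-therapy definition that 16.4.1.1 cites.

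Three stronger readings are tempting and not supported:
- **Substantial laboratory inflation.** In the 3-weekly schedules the last scheduled laboratory, ECG and vital-sign assessments fall at or before the end-of-treatment visit. In Part 2 that visit is normally within 30 (+7) days of last dose or before new therapy. Only unscheduled or late results remain.
- **Dose levels compared over unequal windows.** By-dose tables are for Part 1 only, under one 3-weekly schedule. Part 2 myeloma has a single starting dose and its own tables. Re-consent under amendment 5 is described for ocular follow-up and survival status.
- **A ratio of observation windows as the size of the bias.** The 12-month periods in the SAP concern ocular and survival follow-up. No section gives a year of general AE collection, and a ratio of assumed windows does not measure incidence bias.

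**Conclusion.** The defect is real and internal to the SAP. For medications and blood products, AFTER is an empty category, so the stated restriction removes no record begun after therapy. The end-date rule errs the other way: in a discontinued subject it drops every medication begun before treatment that has a recorded end on or after first dose. These conclusions need only the written rules.

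For AEs and worst-case tables, what holds is that the flag is open-ended and its stop-date note refers to no rule. Any inflation is confined to late-reported AEs, ocular follow-up and unscheduled laboratory results. Its size depends on the protocol's AE reporting period and on what was recorded, so it cannot be stated from the SAP. The point should be corrected, but it does not show that the main AE results are materially biased.

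**What to change.** - **16.4.1:** end On-Treatment at last dose plus a follow-up interval aligned with the protocol's AE reporting period, cut at the start of new systemic anti-cancer therapy. Keep an end-of-treatment visit delayed as footnotes 34 and 26 allow inside the phase when it precedes new therapy. A hard cap at 30 (+7) days would push those results out of the worst-case tables. Add a Post-Treatment phase for everything later.
- **16.4.1.1 and 6.6:** tie DURING, AFTER and the on-therapy window to these phases, and make the end-relative rule test the end date.
- **16.4.2:** apply the same bound to the AE flag, or state that it is deliberately open-ended. Remove the stop-date note or connect it to a rule.
- **Reporting:** show post-treatment AEs, including late corneal events and drug-related SAEs, separately so that none is lost.

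The cost is SAP wording, one derived flag and one extra table. The downside is that, if the AE flag is bounded, some late events move from the main AE table to the separate one.

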5.2. Baseline Definitions

For all endpoints (except as noted in baseline definitions) the baseline value will be the latest pre-dose assessment with a non-missing value, including those from unscheduled visits. If time is not collected, Day 1 assessments are assumed to be taken prior to first dose and used as baseline.

For subjects who did not receive study treatment during the study, baseline will be defined as the latest, non-missing collected value.

For ECG analyses, subject level baseline is defined as the mean of triplicate baseline assessments.

Unless otherwise stated, if baseline data is missing no derivation will be performed and baseline will be set to missing.

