Serum (cytokines/chemokines)		X ¹⁹	X			X ¹⁹	At predose and EOI on D1 of each cycle	X	
Serum (anti-drug-antibodies)	X					X ²⁰	At the start of cycles 3 ²⁰ , 6 ²⁰ , 9 ²⁰ , 12 ²⁰ and 16 ²⁰	X	
Plasma-cfDNA	X							X	
Peripheral blood (flow for TBNK)	X ¹⁵					X ¹⁵	At the start of each cycle ¹⁵	X ¹⁵	
Serial Pharmacokinetics (blood)		X ²¹	X ²¹	X ²¹	X ²¹	X ²¹	C3D1 only ²¹	X ²²	
Urine PK	X ²³					X ²³	Day 1 of cycles 4 ²³ , 7 ²³ , 10 ²³ , 13 ²³ , 16 ²³		
Premedication if needed		X				X	At the start of each cycle		
GSK2857916 administration		X ²⁴				X ²⁴	X ²⁴		
Steroid eye drops		X ²⁵				X ²⁵	X ²⁵		
Adverse Events							Continuous		

Time and Events Table for Full Study (Cycle = 21 days)									
Study Assessments ¹	Screen ²	Day 1 C1	Day 2 C1	Day 8 C1	Day 15 C1	Day 1 C2	D1 of C3-C16	End of Study Treatment	3-Month Off-study Follow-up
Concomitant Medications	X	Continuous							
Survival Status									X ²⁶
Subsequent Treatment									X ²⁶

- Assessments scheduled on days of dosing should be done prior to drug administration, unless otherwise specified. All other assessments can be ± 3 days of scheduled occurrence unless otherwise specified.
- All Screening assessments must be performed within 14 days prior to first dose unless otherwise specified. Informed Consent must be signed before any study-specific assessments are performed.
- Screening examination to include BCVA (best-corrected visual acuity), slit lamp examination (with special focus on cornea), intraocular pressure, and dilated fundoscopic examination may be performed within 21 days prior to first dose.
- On-study exams to include BCVA (best-corrected visual acuity) and slit lamp examination (with special focus on cornea); window for exams is up to 3 days prior to dosing.
- On initial (first infusion) dosing day, vital signs must be assessed at pre-dose (within 30 minutes prior to SOI), +10 minutes and +30 minutes (±5 min) after SOI, EOI, and 1 hour post EOI. On subsequent dosing days, vital signs must be assessed at pre-dose (within 30 minutes prior to SOI), +30 minutes after SOI, and EOI. The Sentinel Subject must be observed for at least 24 hours post EOI. **On days where vital sign timepoints align with PK sampling timepoints, vital signs should be assessed prior to PK samples being drawn.**
- If completed within 72 hrs prior to the first dose, this assessment need not be repeated on Day 1 of Cycle 1. Refer to Table 15 of the protocol for comprehensive list of lab tests.

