- Troponin will be measured at the local lab (troponin I or T) and a central lab (troponin I). CK-MB at the local lab or if not possible by a central laboratory.
- BNP to be measured locally, or if not available by a central laboratory, at screening; if cardiac workup is required due to safety concerns during the study, BNP should be measured.
- Perform only in women of child-bearing potential. A serum pregnancy test should be performed at screening, and subsequent pregnancy tests may be either serum or urine;
- Final pregnancy test (serum or urine) must be performed in women of childbearing potential 60 days after last study treatment.
- On dosing days, ECG to be performed in triplicate at predose (within 30 minutes prior to SOI) and EOI. **On days where ECG timepoints align with PK sampling timepoints, ECGs should be performed prior to PK samples being drawn (PK sample should be taken at the exact nominal time; refer to footnote 21).** At screening, on interim visits (C1D8 and C1D15) and End of Study obtain a single ECG measurement.
- At Screening, LVEF may be performed within 30 days prior to first dose. All ECHOs indicated on dosing days may be performed up to 5 days before dosing. All ECHOs to be done locally and sent to GSK for central imaging storage.
- May be performed up to 21 days prior to C1D1 as screening value. Needs to be performed by the same method throughout the study as was done at baseline (i.e. if PET scan was used as baseline, subject needs to be followed by PET scans). Selected target lesion needs to be measured and followed over time.
- Samples from within 14 days prior to first dose are acceptable.
- Sample(s) collected for analysis by central lab. The same sample will be used for BCMA (flow) and PD during Screening. On D8 only postdose PD assessment will be performed

16. FISH testing at least for: t(4;14), t(14;16), 17p13del. FISH results from samples taken within 60 days prior to first dose are acceptable.
17. Archival tissue from up to 60 days prior to study is acceptable
18. A single sample for sBCMA will be collected at C1D8, C1D15 and at the End of Study visit. sBCMA samples will also be collected on C1D1 at predose (within 30 minutes prior to SOI), at EOI (± 5 minutes) and on C1D2 24h post SOI. On C2D1 sBCMA will be collected pre-dose (within 30 minutes prior to SOI) and at the EOI (± 5 minutes)

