5. On initial (first infusion) dosing day, vital signs must be assessed at pre-dose (within 30 minutes prior to SOI), +10 minutes, +30 minutes (±15 min) after SOI, EOI, and 1 hour post EOI. On subsequent dosing days, vital signs must be assessed at pre-dose (within 30 minutes prior to SOI), +30 minutes after SOI, and EOI. **On days where vital sign timepoints align with PK sampling timepoints, vital signs should be assessed prior to PK samples being drawn.**
6. If completed within 72 hrs prior to the first dose, this assessment need not be repeated on Day 1 of Cycle 1. Refer to Table 15 of the protocol for a comprehensive list of lab tests.
7. Troponin will be measured at the local (troponin I or T) and central (troponin I) lab.
8. CK-MB at the local lab or if not available by a central laboratory.
9. BNP to be measured locally, or if not available by a central laboratory, at screening; if cardiac workup is required due to safety concerns during the study, BNP should be measured.

10. Perform only in women of child-bearing potential. A serum pregnancy test should be performed at screening, and subsequent pregnancy tests may be either serum or urine.
11. Final pregnancy test (serum or urine) must be performed in women of childbearing potential 60 days after last study treatment.
12. ECGs to be performed in triplicate. On dosing days, ECG to be performed at predose (within 30 minutes prior to SOI) and EOI. At screening, on interim visits (C1D8 and C1D15) and End of Study, obtain a single ECG measurement. **On days where ECG timepoints align with PK sampling timepoints, ECGs should be performed prior to PK samples being drawn (PK sample should be taken at the exact nominal time; refer to footnote 24)**
13. At Screening, LVEF may be performed within 30 days prior to first dose. All ECHOs indicated on dosing days may be performed up to 5 days before dosing. ECHOs to be done locally and sent to GSK for central imaging storage.
14. May be performed up to 21 days prior to C1D1 as screening value. Needs to be performed with the same method throughout the study as was done at baseline (i.e. if PET scan was used as baseline, subject needs to be followed by PET scans). Selected target lesion needs to be measured and followed over time.
15. Samples from within 14 days prior to first dose are acceptable.

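### The date-only phase rule labels first-dose ECGs and vital signs taken after the start of infusion as Pre-Treatment, and undefined post-baseline selection leaves open whether worst-case displays keep them.

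*SAP*

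**What the plan says.** SAP section 16.4.1 defines Pre-Treatment as "Date ≤ Study Treatment Start Date" and On-Treatment as "Study Treatment Start Date < Date". It then lists the domains for which Day 1 belongs to the earlier phase: "The first dosing day (Day 1) is considered Pre-Treatment for ECOG, ECG, vital signs, liver events, lab tests, cardiac scan, and other safety" domains. Adverse events and concomitant medications are the only domains for which Day 1 counts as On-Treatment.

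The schedules in Appendix 2 require Day 1 readings on both sides of the first dose. For Part 1: "On dosing days, ECG to be performed in triplicate at predose (within 30 minutes prior to SOI) and EOI". For the Part 2 myeloma cohort: "On dosing days, ECG to be performed at predose (within 30 minutes prior to SOI) and EOI". For vital signs the Part 1 footnote begins "On initial (first infusion) dosing day, vital signs must be assessed at pre-dose (within 30 minutes prior to SOI), +10 minutes and +30 minutes", and goes on to end of infusion and 1 hour after it. The Part 2 myeloma and lymphoma every-3-weeks schedules carry the same time points.

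Section 5.2 uses a different criterion: "the baseline value will be the latest pre-dose assessment with a non-missing value". It treats Day 1 as pre-dose only where no time was collected.

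Section 8.7 and the safety table list in section 16.12.8 define the QTcF and vital-sign worst-case summaries as post-baseline. The SAP does not say whether that means after the section 5.2 baseline or within the section 16.4.1 On-Treatment phase.

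**The concern.** A reading taken at the end of the first infusion follows exposure to drug. Section 16.4.1 nevertheless calls it Pre-Treatment, while under section 5.2 a timed reading of this kind cannot be baseline. Read together, the two rules leave it neither baseline nor On-Treatment.

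Safety is the primary objective, and changes in clinical signs are part of the primary endpoint (section 2.2). The first infusion is given at the assigned starting dose, before any reduction or delay. It is also the only infusion at which vital signs are scheduled at +10 minutes and at 1 hour after the end of infusion; later dosing days ask only for pre-dose, +30 minutes and end of infusion. If the phase flag selects records, those two time points disappear from the worst-case displays for every subject. Two programmers who each follow the SAP could produce different worst-case tables.

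**Working it through.** The plan gives no figure to reproduce, so the check sets the rules against the scheduled time points and counts.

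**Inputs.** Phase rule: section 16.4.1. Baseline rule: section 5.2. Cycle 1 Day 1 time points: ECG and vital-sign footnotes in sections 16.2.2.1, 16.2.3.1 and 16.2.3.3. Worst-case displays: sections 8.7 and 16.12.8.

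**Step 1: classify each Cycle 1 Day 1 time point under both rules, time collected.**

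| Reading | Relative to start of infusion | Phase under 16.4.1 | Status under 5.2 |
|---|---|---|---|
| ECG, pre-dose | before | Pre-Treatment | baseline candidate |
| ECG, end of infusion | after | Pre-Treatment | after baseline |
| Vital signs, pre-dose | before | Pre-Treatment | baseline candidate |
| Vital signs, +10 min | after | Pre-Treatment | after baseline |
| Vital signs, +30 min | after | Pre-Treatment | after baseline |
| Vital signs, end of infusion | after | Pre-Treatment | after baseline |
| Vital signs, 1 h after end of infusion | after | Pre-Treatment | after baseline |

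**Step 2: count.** The two rules disagree for 1 of 2 ECG time points and 4 of 5 vital-sign time points.

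**Step 3: effect on the worst-case displays.** Let S be a subject's readings after the section 5.2 baseline, and D the Day 1 readings after the start of infusion.
- Selection on the section 5.2 baseline uses all of S, and none of D is lost when time is collected.
- Selection on the phase flag uses S without D. Since max(S without D) ≤ max(S), and correspondingly min(S without D) ≥ min(S) for decreases, a worst-case change stays the same or looks milder. The baseline value is the same in both cases, so any bias runs in one direction.

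**Step 4: what remains if the flag selects.** End-of-infusion ECGs and the +30 minute and end-of-infusion vital signs recur on later dosing days. A subject given one dose would lose the only end-of-infusion ECG and all readings taken during the infusion. That subject still has ECGs and vital signs scheduled on Cycle 1 Days 8 and 15 and at the end of treatment, and so would still contribute a worst-case value.

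**Step 5: compare with the rest of the SAP.** Section 16.4.2 tells the analyst to consider clock times for adverse events where collected; no such note covers ECG or vital signs. Section 12.2 computes a QTcF change for each ECG and matches it to concentration by time, and a PK sample is scheduled at the end of the first infusion. Under flag-based selection, the same ECG could count as a change from baseline in the concentration-QTc plot and be absent from the worst-case QTcF table.

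**The case against.** A reader might infer that these readings are certain to be excluded from on-treatment worst-case safety summaries. The SAP does not support that. No ECG or vital-sign worst-case summary is labelled on-treatment; they are labelled post-baseline, and under section 5.2 a timed end-of-infusion ECG is after baseline. Nor does any text say that the phase flag selects these records. Where the SAP wants flags to select data, as for concomitant medications in section 16.4.1.1, it gives the filter explicitly. This part of the objection stands, so the loss is conditional.

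It is also fair that first-dose data appear elsewhere. The concentration-QTc analysis carries no phase restriction, ECG and vital-sign changes by visit are planned, and infusion-related reactions are analysed as adverse events, for which Day 1 is On-Treatment. The date rule also suits laboratory tests: dosing-day assessments precede drug unless otherwise specified, and no chemistry, haematology, coagulation or urinalysis sample is scheduled after the first dose on Cycle 1 Day 1. The point therefore does not extend to labs.

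The objection does not rescue the label. Section 16.4.1 is the only rule that places ECG and vital-sign records in a study phase, it names both domains, and it is wrong for readings taken after the infusion starts. Calling phase and baseline separate concepts does not tell the programmer which of them defines post-baseline.

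**Conclusion.** Wrong as written. Section 16.4.1 mislabels 1 of 2 ECG and 4 of 5 vital-sign time points scheduled on Cycle 1 Day 1, and it does not fit section 5.2. Whether the worst-case QTcF and vital-sign displays lose these readings depends on a choice the SAP leaves open. With the phase flag as selector, all are lost and worst-case changes can be understated; with the section 5.2 baseline as selector, timed readings are kept. The size of any understatement cannot be derived from the SAP; only its direction is fixed. The conclusion rests on the scheduled time points and assumes that a time or planned time point is recorded. The mismatch should be resolved before the safety tables are programmed.

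**What to change.** In section 16.4.1, classify Day 1 ECG and vital-sign records by collected time, or by planned time point, relative to the start of infusion: pre-dose readings as Pre-Treatment, readings after the start of infusion as On-Treatment. Keep the date rule for untimed Day 1 data and for labs. State in section 8.7 that worst-case post-baseline means all records after the section 5.2 baseline, including the Cycle 1 Day 1 readings taken after the start of infusion.

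The cost is a short text change and a small programming change. Section 16.5.2 already makes planned time relative to dosing the basis for summaries, so no new data are needed. Worst-case rates may rise slightly.
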